4.4 Study Conduct Summaries

The number of subjects who were enrolled, treated with at least one dose of study drug, who completed the study, as well as the reasons for withdrawal, will be summarized with counts and percentages by treatment group within each infection study. This table will also include number of screening failures and reasons for screening failures. Protocol violations, inclusion/exclusion criteria, and study drug administration data will also be summarized.

4.5 Determination of Sample Size

Approved labeling, clinical data included in New Drug Applications and approval packages, and sponsor experience with the compounds in this study and similar therapies provide the following estimates and ranges of the cure rates (as proportions) for the treatments within each infection study.

1. BV Subjects
 - a. BV Gel (0.9% metronidazole gel): .50 (.45-.55)
 - b. Placebo Gel: .20 (.15-.25)
2. VVC Subjects
 - a. VVC Gel (0.8% terconazole gel): .70 (.65-.75)
 - b. Placebo Gel: .20 (.15-.25)
3. Mixed Infection Subjects
 - a. Combo Gel (0.9% metronidazole gel and 0.8% terconazole gel): .35 (.30-.40)
 - b. VVC Gel (0.8% terconazole gel): .10 (.05-.15)
 - c. BV Gel (0.9% metronidazole gel): .10 (.05-.15)

Under the assumption that the above estimated cure rates are true for the population, sample sizes were calculated for each infection study based on these estimates for at least 90% power and at least 50 subjects per treatment group. Superiority tests will be performed as two-sided, $\alpha = 0.05$ level significance tests, and sample sizes were calculated using Fisher's Exact test in case the planned Chi-squared test is not appropriate.

The following table provides the sample size required for each treatment group within each infection study. The total sample size is given, and represents the number of evaluable subjects required (Per Protocol population). Entry in each infection study of the trial will be stopped when this number of evaluable subjects is reached, since evaluable/not-evaluable can be determined from the completed case report form prior to unblinding.

Required Number of Evaluable Patients, by Infection Study and Treatment Group							
Study:	BV Only Patients		VVC Only Patients		Mixed Infection Only Subjects		
Treatment Arm:	BV Gel	Placebo Gel	VVC Gel	Placebo Gel	BV Gel	VVC Gel	Combo Gel
Expected Cure Rate	50%	20%	70%	20%	10%	10%	35%
n for at least 80% Power, and at least 50 per group	58	58	50	50	63	63	63
Actual Power	90.0%		> 99.9%		90%		
Total N	405						

Thus, subjects will be enrolled until approximately 405 evaluable subjects, as indicated above, for all three infection studies, have completed the trial.

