4.3 Efficacy Endpoints and Evaluations

The primary and secondary endpoints are reflective of each of the infection studies within the protocol. These include:

Primary Endpoints

- BV Study: BV cure rate, with cure defined as normal/physiologic discharge, negative whiff test, and < 20% clue cells (i.e. clinical cure)
- VVC Study: VVC cure rate, with cure defined as resolution of all signs and symptoms attributable to VVC (i.e. clinical cure)
- Mixed Infection Study: Mixed Infection cure rate, with cure defined as BV cure (i.e. BV clinical cure) AND a VVC cure (i.e. VVC clinical cure)

Primary efficacy endpoint evaluations will occur at the test-of-cure Visit 2.

If a subject requires additional treatment for vaginal discomfort/symptoms (i.e. a BV subject requiring treatment for BV, a VVC subject requiring treatment for VVC or a Mixed Infection subject requiring treatment for BV and/or VVC) prior to or at Visit 2, the subject will be considered a treatment failure. These subjects will be evaluable for the modified intent-to-treat (mITT) and the per-protocol (PP) population analyses, providing all other evaluability criteria for these population groups have been met.

Additionally, if a subject self-medicates herself for vaginal discomfort/symptoms at any time prior to Visit 2, the subject will be considered a treatment failure. If this occurs, the subject will remain evaluable for the mITT analyses but will be non-evaluable for the PP analysis.

Secondary Endpoints

Note, for BV a Gram stain Nugent score cure will be defined as a score of < 4, i.e. 0 – 3.

- BV Study: BV clinical and Gram stain Nugent score combined cure rate, and Gram stain Nugent score cure rate alone; changes/improvements in Amsel criteria and Nugent scores; time to resolution of symptoms
 - In addition, cure rates over time will be explored
- VVC Study: VVC clinical and mycologic cure rates combined and mycologic cure alone; changes/improvements in signs and symptoms scores; eradication (or persistence) of individual fungal species; time to resolution of symptoms
- Mixed Infection Study: BV clinical and Gram stain Nugent score cure rates alone and combined; changes/improvements in Amsel criteria and Nugent scores; VVC clinical and mycologic cure rates alone and combined; changes/improvements in signs and symptoms scores; eradication or persistence of individual fungal species; time to resolution of symptoms

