4.7 Efficacy Analyses

4.7.1 Primary Efficacy Analysis

The primary efficacy endpoint is the cure rate at the test-of-cure visit (Visit 2). Definitions of cure for each of the three infection studies are provided in [Section 4.3](#).

Subjects in all studies will be categorized as cure or failure for the mITT analyses, and as cure, failure or non-evaluable for the PP analysis. The number and percentage of subjects in each treatment group in each of these categories will be reported. Separate statistical analyses will be performed for each of the three infection studies. All treatment comparisons will be based on two-tailed 0.05 significance level hypothesis tests and 95% confidence intervals for the difference in proportion of successes in each treatment. The primary comparison of treatment groups for each study will be performed using a continuity corrected Chi-squared test and Wald continuity corrected confidence intervals. It is anticipated that in some treatment groups in one or more of the infection studies, there may not be sufficient expected cell counts for the Chi-squared test and confidence intervals based on the normal approximation to be

accurate. Therefore, if all expected cell counts are not at least 5, Fisher's Exact test and confidence intervals using the method of Chan and Zhang (1999) will be used.

The primary efficacy analysis for each of the three infection studies will be performed using the mITT population with worst case scenario imputation for missing data. Supportive analyses will also be conducted using the PP population.

Efficacy analysis will not be done for the ITT population, as subjects in the BV and Mixed studies who do not have a gram stain ≥ 4 , or subjects in the VVC and Mixed studies who do not have a positive yeast culture, are not evaluated for efficacy. These subjects do not return for Visit 2; rather, they have the Limited Termination visit for safety evaluations only.

BV Study: The primary statistical objective of the BV infection study is to demonstrate the superiority of BV Gel to Placebo Gel in the treatment of BV. The assessment of superiority will be performed by conducting a continuity corrected Chi-squared test for a difference in the proportion of BV cure between the two treatments. Also, a 95% two-sided confidence interval for the difference in proportion of BV cure between the two treatments will be constructed.

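### The Mixed Infection sample size gives VVC Gel and BV Gel the same 10% cure rate, although the SAP's component rates point to 14% for VVC Gel; the 90% power is then about 74% for Combo Gel vs VVC Gel

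*SAP*

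**What the plan says.** SAP section 4.5 lists planning cure rates, each with a range of plus or minus .05.

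- BV subjects: BV Gel .50, Placebo Gel .20.
- VVC subjects: "VVC Gel (0.8% terconazole gel): .70 (.65-.75" (closing bracket omitted), Placebo Gel .20.
- Mixed Infection subjects: "Combo Gel (0.9% metronidazole gel and 0.8% terconazole gel): .35 (.30-.40" for the combination, "VVC Gel (0.8% terconazole gel): .10 (.05-.15" for terconazole alone, and the same .10 (.05 to .15) for BV Gel.

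Section 4.3 defines the Mixed endpoint as "Mixed Infection cure rate, with cure defined as BV cure (i.e. BV clinical cure) AND a VVC cure (i.e. VVC clinical cure".

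Section 4.5 sizes each infection study "for at least 90% power and at least 50 subjects per treatment group", and says that "sample sizes were calculated using Fisher's Exact test in case the planned Chi-squared test is not appropriate". The table gives 63 evaluable subjects in each Mixed arm and an actual power of 90%. It shows one power figure for the Mixed study, although section 4.7.1 requires Combo Gel to beat each single gel at the 0.05 level.

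The section attributes its rates to labeling, application data and sponsor experience. It does not say how the Mixed rates were obtained.

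**The concern.** In a Mixed subject, each single gel treats one infection and leaves the other to resolve without active drug. The SAP gives unaided cure as 20% for either infection. What separates the two single gels is therefore how well each cures its own target, and there the SAP gives terconazole a 20-point advantage (70% vs 50%). That advantage is absent from the Mixed rates, where both gels stand at 10% with the same range. Section 4.5 does not explain why.

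The consequence is for power. If VVC Gel does better than 10% on the Mixed endpoint, Combo Gel vs VVC Gel is the harder of two comparisons that must both be won, and the plan treats it as no harder than the other. Enrolment stops at the evaluable count, so the planning rates determine the power that the study will have.

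**Working it through.** **Inputs.** From section 4.5: component rates .50, .70, .20 and .20; Mixed rates .35, .10 and .10; 63 per arm; Fisher's exact test; "Superiority tests will be performed as two-sided" at 0.05. Section 4.7.1 confirms "two-tailed 0.05 significance level hypothesis tests" and names the continuity-corrected Chi-squared test as the primary test.

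**Step 1: reproduce the stated power.** Power is the sum, over all pairs of cure counts (i, j) from two independent binomials with n = 63, of the probability of each pair for which the test gives p ≤ 0.05. For .35 vs .10 this is 90.6% with Fisher's exact test and 90.6% with the continuity-corrected Chi-squared test. The stated 90% is reproduced for a single comparison.

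**Step 2: compare the Mixed rates with the component rates.** If the component rates carry over and the two cures are independent within a subject, Mixed cure = BV cure rate × VVC cure rate.

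| Arm | BV cure × VVC cure | Product | SAP |
|---|---|---|---|
| Combo Gel | .50 × .70 | .35 | .35 |
| BV Gel | .50 × .20 | .10 | .10 |
| VVC Gel | .20 × .70 | .14 | .10 |

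Two of the three agree exactly; VVC Gel does not.

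**Step 3: power of Combo Gel (.35) vs VVC Gel at 63 per arm, Fisher's exact test.**

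| VVC Gel Mixed rate | Power |
|---|---|
| .05 (bottom of stated range) | 99.2% |
| .10 (planned) | 90.6% |
| .12 | 83.2% |
| .14 (product) | 73.7% |
| .15 (top of stated range) | 68.4% |

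With the continuity-corrected Chi-squared test, power at .14 is 73.3%.

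**Step 4: power to win both comparisons.** The two comparisons share the Combo Gel arm, so the enumeration runs over all three arms. With Combo Gel .35, VVC Gel .14 and BV Gel .10, it is 70.4% (Fisher) or 70.0% (continuity-corrected). With the SAP's .10 for both single gels it is about 84%; that shortfall from 90% is a separate matter and does not depend on the .14.

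**Step 5: relax independence.** Keep the component rates and apply one common odds ratio between BV cure and VVC cure in every arm.

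| Odds ratio | Combo Gel | VVC Gel | BV Gel | Power, Combo vs VVC Gel (Fisher) |
|---|---|---|---|---|
| 0.33 | .29 | .10 | .06 | 74% |
| 0.5 | .31 | .12 | .07 | 73% |
| 1 | .35 | .14 | .10 | 74% |
| 2 | .39 | .16 | .13 | 77% |
| 3 | .41 | .17 | .14 | 79% |

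An odds ratio of about 0.33 does bring VVC Gel down to .10, but it also moves Combo Gel to .29 and BV Gel to .06, away from the two planned rates that agreed. Nowhere from 0.33 to 3 does the power exceed about 79%.

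**The case against.** A reader might infer that the 90% is a calculation error, or that .10 is shown to be wrong and .14 right. The SAP supports neither. The sizing is conditional on the listed rates, and on those rates the 90% is correct. The product rule is an inference: the rates are attributed to outside sources that this review cannot see.

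Several further points on that side stand.

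- The .14 needs two unstated assumptions: independence, and rates from single-infection subjects that hold in Mixed subjects. The second is open to doubt. Discharge is one of the BV cure criteria, a footnote in section 3.2 recognises that yeast can alter discharge after BV treatment, and a need for treatment of either infection makes a Mixed subject a failure.
- Component rates of .70 and .20 allow any joint rate from 0 to .20. A rate of .10 needs only a modest negative correlation in that arm: (.10 − .14) / √(.70 × .30 × .20 × .80) = −0.22.
- Multiplying the ends of the component ranges gives .29 to .41 for Combo Gel, .07 to .14 for BV Gel and .10 to .19 for VVC Gel. None matches the stated range, and the round point estimates could be rounded judgement.
- The value .14 lies inside the stated range of .05 to .15.

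These points rule out a claim of strict contradiction. They do not explain the equal rates. Rounding .14 to the nearest .05 gives .15, not .10. A dependence between the cures that applies equally in all arms cannot give .35, .10 and .10 together from these component rates; it would have to differ in the VVC Gel arm, and the SAP gives no reason for that. Lying inside the range is also little comfort, because the 90% was calculated only at the point estimate.

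**Conclusion.** The concern holds as an unexplained inconsistency among planning inputs, not as an arithmetic error. The 90% is right for .35 vs .10. For Combo Gel vs VVC Gel it is not supported if the component rates carry over to Mixed subjects and the two cures are independent: power at 63 per arm is then about 74%, and about 70% to win both comparisons. A common odds ratio from 0.33 to 3, still with carried-over component rates, leaves the single-comparison power between about 73% and 79%.

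This affects only the stated power. The primary test, population, endpoint and decision rule are untouched, and a lower power does not weaken a positive result.

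**What to change.** In SAP section 4.5:

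1. Reconcile the VVC Gel Mixed rate with the component rates: either plan .14, or say what supports .10 beside 70% VVC cure and 20% unaided BV cure.
2. Replace the single Mixed power entry with one per comparison at 63 per arm: about 90% for Combo Gel vs BV Gel at .10; for Combo Gel vs VVC Gel, about 74% at .14 shown next to about 90% at .10. State the carry-over and independence assumptions behind the .14.
3. State that the claim of at least 90% power for the Mixed study does not hold for Combo Gel vs VVC Gel at .14 with 63 per arm.

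The cost is a few sentences, one table entry and a less favourable stated power. N need not change if the power claim is restated. Keeping 90% for that comparison at .14 would instead take about 94 evaluable subjects per arm with Fisher's exact test (power 90.35%), or 3 × (94 − 63) = 93 more across the three arms.

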VVC Study: The primary statistical objective of the VVC infection study is to demonstrate the superiority of VVC Gel to Placebo Gel. The assessment of superiority will be performed by conducting a continuity corrected Chi-squared test for a difference in the proportion of VVC cure between the two treatments. Also, a 95% two-sided confidence interval for the difference in proportion of VVC cure between the two treatments will be constructed.

Mixed Infection Study: The primary statistical objective of the Mixed Infection Study is to demonstrate the superiority of the Combo Gel to both BV Gel and VVC Gel. The assessment of superiority will be performed by conducting a continuity corrected Chi-squared tests for a difference in the proportion of Mixed Infection cure between the Combo Gel and each of the two single entity treatments. If the P-values for both of the hypothesis tests are less than or equal to 0.05, the Combo Gel will be considered superior to both of the single entity gels. Despite there being two comparisons made within the same study, no adjustment for multiplicity is necessary since both comparisons must be positive instead of "at least one," in order to conclude superiority of the Combo Gel. Also, 95% two-sided confidence intervals for the difference in proportion of Mixed Infection cure between the Combo Gel and each of the two single entity treatments will be constructed.

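### The 90% power tabled for the Mixed Infection Study applies to one comparison; requiring both to succeed gives about 84%, and the table's 80% row label contradicts the 90% target in the text.

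*SAP*

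**What the plan says.** Section 4.5 sets out assumed cure rates for each infection study and states that "sample sizes were calculated for each infection study based on these estimates for at least 90% power", with a minimum of 50 per group, two-sided tests at 0.05, and Fisher's exact test as the sizing method. For the Mixed Infection Study the assumed rates are 0.35 for Combo Gel and 0.10 for each single-entity gel. The table gives 63 evaluable subjects per arm and an actual power of 90%. The row holding these sample sizes is labelled "n for at least 80% Power, and at least 50 per group".

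Section 4.1 makes the objective of this study superiority of Combo Gel to both single-entity gels. Section 4.7.1 turns that into a decision rule: "If the P-values for both of the hypothesis tests are less than or equal to 0.05, the Combo Gel will be considered superior". The same paragraph relies on the rule to leave alpha unadjusted: "no adjustment for multiplicity is necessary since both comparisons must be positive".

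The sample sizes in section 4.5 count evaluable (Per Protocol) subjects, whereas under section 4.7.1 the primary analysis "will be performed using the mITT population with worst case scenario imputation for missing data".

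**The concern.** Requiring both comparisons to be significant protects the type I error without an alpha adjustment, but it costs power: the study fails if either comparison fails. Section 4.7.1 takes the benefit of the rule, and nothing in section 4.5 shows that the cost was counted. In the BV and VVC columns the actual-power entry is the probability of meeting the whole objective of that study, so a reader will take the Mixed Infection entry the same way. If it is a per-comparison figure, the power for the study's own success criterion is overstated.

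The section also names two targets, 90% in the text and 80% in the row label. Both cannot describe the calculation behind the tabled numbers.

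**Working it through.** **Inputs.** From section 4.5: 63 per arm; cure rates 0.35 (Combo Gel), 0.10 (BV Gel) and 0.10 (VVC Gel); sizing by Fisher's exact test. From section 4.7.1: "two-tailed 0.05 significance level hypothesis tests"; continuity-corrected Chi-squared test as the primary test, with Fisher's exact test if any expected count is below 5; success only if both P-values are at most 0.05.

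**Step 1: the plan's own figure.** Let *c* and *b* be the numbers cured on Combo Gel and on one single-entity gel. Power for one comparison is

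Σ_c Σ_b Bin(c; 63, 0.35) × Bin(b; 63, 0.10) × I(c, b),

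where I(c, b) = 1 if the two-sided P-value is at most 0.05 and c > b. Summing over all outcomes gives 90.6% with Fisher's test and 90.6% with the planned rule. The tabled 90% is therefore reproduced as a per-comparison power. The other columns also agree: BV at 58 per arm (0.50 vs 0.20) gives 90.6% against 90.0% stated, and VVC at 50 per arm (0.70 vs 0.20) gives 99.94% against more than 99.9% stated. The total is right: 2 × 58 + 2 × 50 + 3 × 63 = 405.

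**Step 2: power for the stated rule.** Both comparisons share the Combo Gel arm, so they are positively correlated. Given *c*, they are independent. Let g(c) = Σ_b Bin(b; 63, 0.10) × I(c, b). The two single-entity gels have the same assumed rate, so

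joint power = Σ_c Bin(c; 63, 0.35) × g(c)².

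| Test | One comparison | Both comparisons |
|---|---|---|
| Fisher's exact | 90.6% | 84.5% |
| Planned rule (corrected Chi-squared, Fisher fallback) | 90.6% | 84.4% |

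A simulation of 2,000,000 trials gives 84.49% and 84.39% for both comparisons. Treating the comparisons as independent would give 0.906² = 82.1%; the shared arm raises this by about two points. The shortfall from 90% is 90.0 − 84.5 = 5.5 points, and the chance of missing the criterion is 100 − 84.5 = 15.5%.

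**Step 3: which target produced the tabled sample sizes.** Smallest n per arm with Fisher's test:

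| | 80% target | 90% target | Tabled n |
|---|---|---|---|
| BV | 44 (80.2%) | 58 (90.6%; 57 gives 89.96%) | 58 |
| Mixed, one comparison | 49 (80.9%) | 62 (90.02%) | 63 |
| Mixed, both comparisons | 58 (80.7%) | 72 (90.3%; 71 gives 89.8%) | 63 |

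Under an 80% per-comparison target the floor of 50 would have applied to both studies. The tabled 58 is exactly the 90% answer for BV. The tabled 63 is within one subject of the 90% per-comparison answer for Mixed Infection and matches neither joint answer. The 80% label is the error, and the Mixed Infection size was set per comparison.

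**Step 4: could another test explain the 90%?** The uncorrected Pearson Chi-squared test comes closest, with joint power 89.1% at 63 per arm. The SAP neither sizes with it nor plans it for the primary analysis, and it would give 93.3% for BV, not the stated 90.0%.

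**The case against.** The best reply is that the 90% is a correct number lacking a label. Section 4.5 speaks of superiority tests one at a time and never says that 90% is the probability of winning both. Joint power of 84% still clears the 80% in the row label. The Introduction describes the study as already conducted, so a better power statement changes no estimate, test or decision. It is true that the per-comparison calculation is sound and that the practical consequence is small. But the text promises 90% for each infection study, and for this one the objective is superiority to both gels. Nor does 63 follow from an 80% joint target, which needs 58.

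A second reply is that 84% is itself conditional, which is also true. It applies to 63 subjects per arm at the point-estimate rates. The primary analysis is mITT with missing outcomes counted as failures, and entry stops on the evaluable count, so the mITT arms should be larger. The SAP gives no non-evaluable rate. If one assumes 70 mITT subjects per arm, joint power is roughly 82 to 83% when the seven extra subjects per arm all fail, and about 89% when they cure at the assumed rates. At an assumed 74 per arm the corresponding figures are roughly 82 to 83% and about 91%.

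The assumed rates matter more. Joint power at 63 per arm (Fisher) across the SAP's own ranges:

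| Combo / single gels | Joint power |
|---|---|
| 0.30 / 0.15 / 0.15 | 28.5% |
| 0.35 / 0.15 / 0.15 | 54% |
| 0.30 / 0.10 / 0.10 | 64% |
| 0.35 / 0.05 / 0.10 | 90.3% |
| 0.40 / 0.10 / 0.10 | 95% |
| 0.35 / 0.05 / 0.05 | 98.5% |

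This spread dwarfs a 5.5-point gap and limits its practical weight. It does not make the tabled 90% right at the rates for which it is stated.

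The two power targets should not be overstated as a problem either: a careful reader can infer from the numbers that 90% was used.

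**Conclusion.** Both parts hold. At the SAP's point-estimate rates and 63 evaluable subjects per arm, the tabled 90% is the power of one comparison; power for the success rule in section 4.7.1 is 84.4 to 84.5%. The 80% row label contradicts the text and does not fit the tabled numbers. The result rests on exact binomial calculation with the tests that the SAP names, and on the Per Protocol count that the SAP itself uses for sizing. Power in the mITT primary analysis may be lower or higher. The absence of a multiplicity adjustment is justified, and type I error is unaffected. This is a misstated power for a primary objective that should be corrected; it does not threaten the analysis.

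**What to change.** Three wording changes in section 4.5:

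1. State both powers for the Mixed Infection Study, for example: *63 evaluable subjects per arm give 90.6% power for each comparison of Combo Gel with a single-entity gel, and about 84% power that both comparisons are significant.*
2. Change the row label from 80% to 90%, and mark it as per comparison for the Mixed Infection Study.
3. Add that the power figures refer to the Per Protocol count, while the primary analysis is mITT, where power may be lower or higher depending on the number and outcomes of non-evaluable subjects.

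No subjects, tests or alpha levels change. For scale only: 90% joint power would have needed 72 per arm, which is 3 × 72 = 216 instead of 189 in this study, or 27 more (432 instead of 405 overall). That increase is not requested. The only cost is a less favourable stated power for the Mixed Infection Study.
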